## 11. Pharmacokinetics

### 11.1 Plasma Drug Concentrations of Naldemedine and Nor-naldemedine

Plasma drug concentrations of naldemedine and nor-naldemedine will be listed for the PK-C Population and summarized for the PK-P Population by actual treatment group, and nominal sampling time with the number of nonmissing observations (N), arithmetic mean (mean), standard deviation (SD) and coefficient of variation (CV%, calculated by  $SD/\text{mean} \times 100$ ), geometric mean and coefficient of variation for geometric mean (Geometric CV%), and median, minimum and maximum values at each sampling time presented. The Geometric CV% will be calculated as follows:  $\text{Geometric CV\%} = [\exp(\text{sd}^2) - 1]^{1/2} \times 100$ , where SD is the standard deviation for natural log (ln)-transformed data. The time course profiles for plasma drug and metabolite concentrations will be presented graphically.

For the summary of plasma drug and metabolite concentrations, concentrations below the limit of quantification (BLQ) will be treated as zero (0) for calculations of the mean, SD, CV%, and median, minimum, maximum values and will be treated as missing for calculation of the geometric mean and geometric CV% values.

Data will be summarized by nominal sampling time, using the following times:

- Day 2 immediately before the morning dose
- Day 3 immediately before the morning dose and 1 hour and 2, 4, 8, and 12 hours after the morning dose before administration of the evening dose
- Day 4 immediately before the morning dose

### 11.2 PK Parameters for Naldemedine and Nor-naldemedine on Day 3

The PK parameters will be estimated using the PK-P Population. The following PK parameters will be calculated, whenever possible, for naldemedine and nor-naldemedine from plasma concentration data on Day 3 (immediately before the morning dose and 1 hour and 2, 4, 8, and 12 hours after the morning dose before administration of the evening dose) by noncompartmental methods. Other parameters may be computed, as appropriate, upon review of the data. The following estimated PK parameters will be computed for each study patient using the actual sample collection times:

- $C_{\max}$  – maximum observed plasma concentration on Day 3
- $T_{\max}$  – time to maximum plasma concentration on Day 3. If  $T_{\max}$  is the actual time for the predose (0 hours) on Day 3,  $T_{\max}$  will be calculated as 0.
- $AUC_{0-\tau}$  – area under the concentration- time curve over the dosing interval  $\tau$  (12 hours) on Day 3; calculated by linear up/log down trapezoidal method.  $AUC_{0-\tau}$  will

be calculated with observed plasma concentrations from time 0 to  $\tau$  (actual time) on Day 3 without extrapolation or interpolation. The actual time for the predose (0 hours) on Day 3 will be replaced with 0. If the observed plasma concentration at  $\tau$  on Day 3 is BLQ, the area under the plasma concentration-time curve from time zero to the time of the last quantifiable concentration after dosing ( $AUC_{0-\text{last}}$ ) will be used as  $AUC_{0-\tau}$ .

- CL/F – apparent total clearance estimated as  $CL/F = \text{dose}/AUC_{0-\tau}$  on Day 3 (for naldemedine only)
- $MR_{M/U, C_{\max}}$  – metabolic ratio of  $C_{\max}$  of nor-naldemedine to  $C_{\max}$  of naldemedine, corrected for molecular weight, defined as:
  - $$\frac{C_{\max} \text{ of nor-naldemedine}}{C_{\max} \text{ of naldemedine}} * \frac{570.64}{516.55}$$
(for nor-naldemedine only)
- $MR_{M/U, AUC}$  – metabolic ratio of  $AUC_{0-\tau}$  of nor-naldemedine to  $AUC_{0-\tau}$  of naldemedine, corrected for molecular weight, defined as:
  - $$\frac{AUC_{0-\tau} \text{ of nor-naldemedine}}{AUC_{0-\tau} \text{ of naldemedine}} * \frac{570.64}{516.55}$$
(for nor-naldemedine only)

The estimated PK parameters except for  $T_{\max}$  will be summarized by actual treatment group with N, mean, SD, CV%, geometric mean, geometric CV%, median, minimum and maximum values. The  $T_{\max}$  will be summarized by analyte and dosing regimen with N, mean, SD, CV%, median, minimum and maximum values. If the number of patients with PK parameter data is < 3, the data will not be summarized.

Individual plasma concentrations, if deemed to be anomalous, may be excluded from the analysis at the discretion of the PK study director. Any such exclusion will be disclosed in the study report along with the justification for exclusion.

For the calculations of PK parameters, BLQ before the occurrence of the first quantifiable concentration on Day 3 will be treated as zero, and BLQ after the first occurrence of the quantifiable concentration on Day 3 will be treated as missing.

Pharmacokinetic calculations will be performed by using WinNonlin Version 6.2.1 or higher.

## 12. INTERIM ANALYSES

A Data Monitoring Committee (DMC) will review all data when assessing the benefit versus risk of the ongoing results. Since such a review may include efficacy data, an alpha spending function will be included in the DMC charter that allows for a small spend of alpha that will not impact on final alpha assessment level (eg, an alpha spend of 0.0001 based on Haybittle-Peto could be used to control alpha for each interim analysis). The DMC charter will specify the spending function to be used.

In addition, depending on the enrollment rate, an interim analysis of efficacy may be feasible. Based on the operational feasibility of such an interim analysis, the interim analysis could include a non-binding futility assessment. For example, should the enrollment project that 85 patients per group is achievable and an interim analysis based on 44 patients per group can be conducted in a timely and worthwhile fashion prior to the last patient enrolled, then the DMC will review the interim analysis results. Details for interim analyses, including futility, will be provided in the DMC Charter, and/or an accompanying DMC Statistical Analysis Plan.

## 13. PROGRAMMING CONVENTIONS

### 13.1 Formatting and Programming Rule

Unless otherwise noted, the following conventions should be used when constructing the TFLs:

- Every summary table and figure will clearly specify the analysis population being summarized. Listings will be prepared for all patients randomized.
- Rounding for all variables will occur only as the last step, immediately prior to presentation in TFLs. No intermediate rounding will be performed on derived variables. The standard rounding practice of rounding numbers ending in 0-4 down and numbers ending in 5-9 up will be employed.
- The presentation of numerical values will adhere to the following guidelines:
  - Raw measurements will be reported to the number of significant digits as captured electronically or on the CRFs.
  - Means, SDs, minimums, medians, and maximums will be reported to 1 decimal place beyond the number of decimal places with which the original endpoint is presented.
  - Calculated percentages will be reported to 1 decimal place.
  - Calculated hours will be presented to 2 decimal places.
- All means presented will be arithmetic unless otherwise stated.
- For PK concentrations and PK parameters,
  - Arithmetic mean, geometric mean, median, minimum, and maximum will be presented to the same precision as raw data
  - Standard deviation will be presented to the same precision as the arithmetic mean
  - Coefficient of variation (%) and coefficient of variation (%) for geometric mean will be presented with one decimal place.
  - Individual actual date and time of study treatment dosing, meal prior to dosing, and PK sampling will be reported with the same format as the source data.
  - Individual actual time (i.e., the difference between dosing and PK sampling time) for PK analysis will be reported with two decimal places.

- Individual concentrations will be reported with the same precision as the source data.
- Individual PK parameters  $C_{max}$  will be reported with the same precision as the source data.
- Individual PK parameters  $T_{max}$  will be reported with two decimal places
- Individual PK parameters  $AUC_{0-\tau}$  will be reported with four significant digits.
- Individual PK parameters  $CL/F$  will be presented to three significant digits.
- Individual PK parameters  $MR_{M/U, C_{max}}$  and  $MR_{M/U, AUC}$  will be presented with three decimal places.
- Table 7 shows the category displayed in analysis and summary.

**Table 7 Category**

Data	Category
Age	18<= x < 65, 65 < x < 74, 75<=x<=80
Sex	Male, Female
Surgical procedure	Small bowel resection with primary anastomosis, large bowel resection with primary anastomosis, or radical cystectomy requiring bowel transection with primary anastomosis
Fertility status for females	Surgically sterile, post-menopausal, potentially able to bear children
Race	American Indian or Alaska Native, Asian, Black or African American, Native Hawaiian or Other Pacific Islander, White, Other, Not provided
Ethnicity	Hispanic or Latino, Not Hispanic or Latino, Unknown, Not provided
Elements of the enhanced recovery protocol	(required) Early removal of the nasogastric tube defined as removal of the nasogastric tube at the end of surgery, early ambulation defined as ambulation on Day 1, early diet advancement on Day 1  (non-required) Antibiotic prophylaxis, preoperative carbohydrate drink, epidural anesthesia in addition to general anesthesia, chewing gum postoperatively
Elements of the enhanced recovery protocol (binary)	All non-required (defined as all of 4 non-mandated ERP elements), not all non-required (defined as otherwise all non-required)
Epidural anesthesia	Yes (defined as Yes in epidural anesthesia in addition to general anesthesia in ERP), No (defined as No in epidural anesthesia in addition to general anesthesia in ERP)
Prior surgery	No prior surgery, 1 prior surgery and 2 prior surgeries
Treatment compliance	x <80%, 80% <= x <=100%, 100% < x

## 13.2 Sample SAS Code

When dataset A has time of GI2 and censored information, there are mainly 3 steps to calculate RMST.

(1) GI2 after 240 hours should be censored before calculating RMST until 240 hours.

```
DATA B;  
SET A;  
  IF (hour > 240) then status=0;  
RUN;
```

(2) The program below will provide  $\hat{\mu}_{kg}(t)$  in the dataset C0. The number of GI2 (saved in a variable ‘Failed’) will be given in the dataset C1, where hour is GI2 time, status=0 if censored, 1 if not censored, surgery is surgery procedure, treatment is treatment group.

```
ODS OUTPUT MEANS=C0 CENSOREDSUMMARY=C1;  
PROC LIFETEST DATA=B TIMELIM=240;  
  BY surgery;  
  TIME hour*status (0);  
  TEST treatment;  
RUN;
```

(3) Standard deviation of each RMST  $\sqrt{Var[\hat{\mu}_{kg}(t)]}$  will be given as ‘sd’. The test statistics T and S defined in section 9.1.1 will be calculated by these estimates of RMST and SDs.

[figure not shown]
```
DATA D;  
MERGE C0(IN = A) C1;  
BY treatment surgery;  
sd = StdErr *SQRT((Failed – 1)/Failed);  
IF A;  
RUN;
```

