#### 9.1.1 Primary Analysis

The primary objective is to compare the efficacy of naldemedine 1.25 mg, 2.5 mg, and 5 mg and placebo for the primary endpoint.

Let  $\hat{\mu}_{kg}(t)$  be the estimate of RMST at time  $t$  for the surgical procedure  $k$  ( $k=1,2,3$ ) and treatment group  $g$  ( $g=1,2,3,4$ ). Let  $\hat{\mu}_k(t) = (\hat{\mu}_{k1}(t), \hat{\mu}_{k2}(t), \hat{\mu}_{k3}(t), \hat{\mu}_{k4}(t))^T$  be the vector of estimates of RMST for surgical procedure  $k$ .  $c = (-3, -1, 1, 3)^T$  is defined as contrast coefficient. The null hypothesis will be

$$H_0: c^T \mu_1(t) = c^T \mu_2(t) = c^T \mu_3(t) = 0$$

and test statistics  $T$  will be

$$T = \frac{\sum_{k=1}^3 c^T \hat{\mu}_k(t)}{\sqrt{\sum_{k=1}^3 \{Var[c^T \hat{\mu}_k(t)]\}}}$$

, where

$$Var[c^T \hat{\mu}_k(t)] = 9 * Var[\hat{\mu}_{k1}(t)] + 1 * Var[\hat{\mu}_{k2}(t)] + 1 * Var[\hat{\mu}_{k3}(t)] + 9 * Var[\hat{\mu}_{k4}(t)]$$

Therefore p-value will be

$$2\{1 - \Phi(|T^{obs}|)\}$$

, where  $\Phi(\cdot)$  will be standard normal distribution and  $T^{obs}$  will be the observed test statistics.

For pairwise comparison between treatment groups i and j (i, j = 1, 2, 3, 4), the null hypothesis will be

$$H_0: \mu_{1i}(t) - \mu_{1j}(t) = \mu_{2i}(t) - \mu_{2j}(t) = \mu_{3i}(t) - \mu_{3j}(t) = 0$$

and test statistics S will be

$$S = \frac{\sum_{k=1}^3 \{\hat{\mu}_{ki}(t) - \hat{\mu}_{kj}(t)\}}{\sqrt{\sum_{k=1}^3 \{Var[\hat{\mu}_{ki}(t)] + Var[\hat{\mu}_{kj}(t)]\}}}$$

- 1) The mean survival time, which is also referred to as the RMST, of GI2 events within 240 hours will be estimated using the area under the Kaplan-Meier (KM) curve. To demonstrate the linear dose-response relationship between treatment groups (3 naldemedine groups and placebo group) and the RMST, the linear contrast test for trend with contrast coefficients of (-3, -1, 1, 3) will be performed based on the test statistics T described above. Two types of KM curve with 95% confidence bound and point estimate line only will be provided. SAS code will be provided in section 13.2.
- 2) Pairwise comparisons of all treatments will be undertaken based on the test statistics S described above and the differences of treatment means including their 95% confidence interval (CI) will be calculated as

$$\frac{1}{3} \sum_{k=1}^3 \{\hat{\mu}_{ki}(t) - \hat{\mu}_{kj}(t)\} \pm z_{\alpha/2} \times \frac{1}{3} \sqrt{\sum_{k=1}^3 \{Var[\hat{\mu}_{ki}(t)] + Var[\hat{\mu}_{kj}(t)]\}}$$

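### The sample SAS code in SAP 13.2 for the primary analysis groups by surgical procedure only, so it gives 3 pooled RMSTs instead of the 12 procedure-by-treatment values it is said to give

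*SAP*

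**What the plan says.** SAP 9.1.1 defines the primary test from RMST estimates indexed by surgical procedure (k = 1, 2, 3) and treatment group (g = 1, 2, 3, 4). The trend test with "contrast coefficients of (-3, -1, 1, 3) will be performed based on the test statistics T described above". For the second set of tests, "Pairwise comparisons of all treatments will be undertaken based on the test statistics S described above". On implementation, the section states: "SAS code will be provided in section 13.2".

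SAP 13.2 then sets out three steps.

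- Step 1 censors events after 240 hours.
- Step 2 calls "PROC LIFETEST DATA=B TIMELIM=240" and saves two tables with "ODS OUTPUT MEANS=C0 CENSOREDSUMMARY=C1". The accompanying text says that C0 will hold the RMST indexed by both k and g, and that C1 will hold the number of GI2 events in a variable called Failed. The grouping statement is `BY surgery`. Treatment enters only through "TEST treatment". There is no STRATA statement anywhere in the code.
- Step 3 merges C0 and C1 "BY treatment surgery" and derives a standard deviation for each RMST as StdErr × √((Failed − 1)/Failed). The text closes the loop: "The test statistics T and S defined in section 9.1.1 will be calculated by these estimates of RMST and SDs".

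**The concern.** The text around the code promises a procedure-by-treatment result, and the code in step 2 does not ask for one. A BY statement on surgery alone gives one analysis per procedure. Naming treatment on a TEST statement makes it a covariate for a rank test of association and leaves all four arms pooled in a single Kaplan-Meier curve. Step 3 shows that output by treatment was intended, because it merges on treatment. This is therefore a slip and not a different method.

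The stake is the reproducibility of the documented primary analysis. Section 9.1.1 writes T, S and the confidence interval in terms of a variance for each cell but does not say how that variance is estimated. Section 13.2 is the only place that does, so the code carries part of the specification. The reach is also wider than one endpoint: SAP 9.2.1.1 (discharge order), 9.3.1.1 (discharge readiness) and 9.3.2.1 (actual discharge) all refer back to 9.1.1 for their method.

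**Working it through.** The plan states no figure to reproduce here. The check traces the code against the formulas in 9.1.1.

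**1. What T and S need.** T sums the contrast c′μ̂ₖ over the three procedures, with c = (−3, −1, 1, 3), and divides by the square root of the summed contrast variances. Each contrast variance is 9·Var(μ̂ₖ₁) + Var(μ̂ₖ₂) + Var(μ̂ₖ₃) + 9·Var(μ̂ₖ₄). S uses differences between cells of the same procedure. Inputs required: 3 × 4 = 12 RMSTs and 12 variances.

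**2. What step 2 produces as printed.** Grouping variables: surgery only, 3 levels. Output: 3 × 1 = 3 RMSTs, 3 standard errors and 3 event counts, each pooled over the four arms. The TEST statement adds rank tests and no further rows to the means table.

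**3. What step 3 needs.** Merging on treatment and surgery requires both variables in C0 and in C1. Step 2 puts surgery in both and treatment in neither, so the merge lacks one of its keys.

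**4. Could the pooled rows stand in for the cells?** No. If the pooled mean m for a procedure were assigned to all four arms, the contrast would be (−3 − 1 + 1 + 3) × m = 0. T would be 0 whatever the data, and every pairwise difference in S would be 0. Nothing in the SAP proposes this; it only shows that the pooled output carries no information on treatment.

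**5. The variance factor.** √((Failed − 1)/Failed) is meant to use the event count of the cell. As printed, Failed is the pooled count for the procedure, and StdErr is pooled as well. With assumed counts, for illustration only:

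| Failed | Calculation | Factor |
|---|---|---|
| 5 (one cell) | √(4/5) | 0.894 |
| 20 (four such cells pooled) | √(19/20) | 0.975 |

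The two factors differ, so the count must come from the right level.

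**6. After correction.** With treatment as a grouping variable, step 2 gives 3 × 4 = 12 rows if every cell is populated. A Python emulation of the Kaplan-Meier area to 240 hours on one invented dataset gave 12 estimates under the corrected grouping, and T could then be calculated. Under the printed grouping it gave 3 estimates, with a contrast of 0.0 in each procedure when the pooled value was used for all arms. The invented data show only that T becomes computable.

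**The case against.** The strongest reply is that this is sample code under programming conventions and that the plan does not depend on it. Section 9.1.1 gives T, S, the p-value and the confidence interval by formula, and defines the RMST as the area under the Kaplan-Meier curve to 240 hours. A merge on an absent variable should fail openly and not return a plausible wrong p-value. Most of this stands.

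It also disposes of two stronger readings that a reader might infer. One is that the primary test statistics cannot be formed at all. The documents do not support that: the formulas are independent of the code, and any correct grouping gives the same 12 estimates. The other is that a repair would fall outside the plan. It would not: section 13.2 itself says that the output is indexed by procedure and treatment, so aligning the code carries out the stated intention. SAP section 1 in any case requires deviations from the final SAP to be documented in the clinical study report.

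Three further limits are fair.

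- The reading of TEST versus STRATA rests on standard SAS behaviour, which the documents do not describe, and the program was traced and emulated but not run in SAS. The mismatch between the step 2 grouping and the step 3 merge keys is nevertheless visible on the page.
- `STRATA treatment` is not the only remedy.
- Content is missing just before the step 3 code in the text available, so the absence of a sort cannot be counted as an error. A sort could not, however, supply a treatment variable that step 2 did not output.

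What does not stand is that the slip is purely cosmetic. Section 9.1.1 refers to this code for the primary analysis, and the code alone states how the cell standard deviation is obtained.

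**Conclusion.** The point holds as an error in the code. As printed, step 2 yields 3 pooled RMSTs and 3 pooled event counts where section 13.2 says that it yields a value for each of 12 procedure-treatment cells, and step 3 then merges on a variable that is not there. The defined test and the RMST it rests on are sound. No effect on type I error, power or bias is shown, and none is claimed. The conclusion assumes standard PROC LIFETEST behaviour for TEST and BY statements; the figure of 12 assumes that every cell contains patients. It merits correction because it sits in the documented primary analysis and in the only statement of the cell standard deviation. It is not a threat to the validity of the trial.

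**What to change.** Before unblinding, correct SAP 13.2 as follows.

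- In step 2, make treatment a grouping variable: either replace the TEST statement with `STRATA treatment` and keep `BY surgery`, or use `BY surgery treatment` on data sorted in that order.
- Make sure that C0 and C1 are ordered by the step 3 merge keys. Either correction gives output ordered by surgery and then treatment, while the merge lists treatment first. If the full SAP already shows a sort at that point, nothing needs adding.
- Add a check that C0 has one row per populated procedure-treatment cell (12 if all are populated) and that Failed is the event count of that cell.

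The cost is about one line of code, a possible sort and a row-count check. No formula, endpoint or sample size changes, and no analytic discretion is opened. Protocol 9.4 already provides for the SAP to be finalized before unblinding and database lock, so the correction fits the planned process.
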